15.5 Vital Signs

Population: SAF Analysis Set

Body temperature, SBP, DBP, respiratory rate and heart rate will be analyzed with shift tables of maximum CFB of on-treatment assessments using the categories defined below:

Table 13 Vital signs categories

Parameter	Unit	Shift	Baseline categories	On-treatment categories (absolute change)
Temperature	°C	Increase	< 37 / ≥ 37 - < 38 / ≥ 38 - < 39 / ≥ 39 - < 40 / ≥ 40	< 1 ^a / ≥ 1 - < 2 / ≥ 2 - < 3 / ≥ 3
Heart rate	Bpm	Increase and decrease	< 100 / ≥ 100	≤ 20 ^a / > 20 - ≤ 40 / > 40
SBP	mmHg	Increase and decrease	< 140 / ≥ 140	≤ 20 ^a / > 20 - ≤ 40 / > 40
DBP	mmHg	Increase and decrease	< 90 / ≥ 90	≤ 20 ^a / > 20 - ≤ 40 / > 40
Respiratory rate	breaths/min	Increase and decrease	< 20 / ≥ 20	≤ 5 ^a / > 5 - ≤ 10 / > 10

a This category will include the subjects with no changes or decrease/increase in the increase/decrease part of the table, respectively.

Line plots per dose level and overall will be produced for systolic blood pressure, diastolic blood pressure, heart rate, temperature and weight. These will be presented by visit.

Maximum change from baseline will also be listed for each parameter and participant and will include: Dose level, subject ID, parameter, visit, date, unit, baseline value and maximum change from Baseline for each participant. This listing will be sorted by dose level, subject ID, parameter and visit.

Finally, all vital signs data from “Vital Signs” eCRF pages will be listed.

15.6 Other Safety or Tolerability Evaluations

15.6.1 ECOG Performance Status

Population: SAF analysis set

The listing will include all the data from the “ECOG Performance Status” eCRF section.

Additionally, one spaghetti plot per dose level will be produced, using different colors/line types per participant.

15.6.2 ECG and QT/QTc Evaluations

Population: SAF analysis set

Electrocardiogram values based on the “Electrocardiogram” eCRF section will be used for summary statistics and shift tables.

ECG parameters (Heart Rate, R-R duration, PQ/PR duration, QT duration, QR duration, QTcF) will be summarized by dose level and visit, using descriptive statistics (see [Section 9](#)) for absolute values and absolute change from baseline.

The number of participants with normal ECGs at baseline and abnormal ECGs post baseline will be calculated by visit and summarized in a frequency table by dose level and overall. In addition, ECG parameters on treatment will be presented by the following frequency table (by dose level and overall):

- Shift from normal baseline result to the worst on-treatment value
 - ≤ 450 ms
 - > 450 ms and ≤ 480 ms
 - > 480 ms and ≤ 500 ms
 - > 500 ms
- Worst on treatment mean QTcF increase from baseline
 - ≤ 30 ms
 - > 30 ms and ≤ 60 ms
 - > 60 ms

If duplicate/triplicate measurements are performed at any time point, the following will apply:

- For quantitative parameters, the mean of the triplicate measurement will be used as summary
- For results interpretation, the worst Overall conclusion will be retained.

Visits and time points to be displayed in summary tables are all scheduled visits where ECG assessments are performed.

Two listings will display all the results as presented in “ECG” eCRF page, one on qualitative results and another one on quantitative results. All visits, time points, flag for pre /on /post treatment, and, in case of triplicates, mean for quantitative results and worst overall conclusion for qualitative results, will be included in listings.

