8.2.3 Electrocardiograms

Digital ECGs for all participants will be recorded at the site. Triplicate ECGs will be obtained for participants according to the Schedules of Activities (Table 1).

Electrocardiograms will be documented by recording date and time of collection. All ECG results must be reviewed at the site by the Investigator or a medically qualified designee for clinical management of the participant. The Investigator will judge the overall interpretation as normal or abnormal. If abnormal, it will be decided if the abnormality is clinically significant or not clinically significant and the reason for the abnormality will be recorded on the eCRF.

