Occurrence of abnormalities (Grade ≥ 3) in laboratory test values and markedly abnormal vital sign measurements, and clinically significantly abnormal ECGs including clinically important increases in QT interval (QTcF)	Laboratory results will be classified by grade according to NCI-CTCAE v5.0. The worst on-study grades after the first study intervention will be summarized. Shifts in toxicity grades from first treatment to highest grade will be displayed. Results for variables that are not part of NCI-CTCAE will be presented as below, within, or above normal limits. Only participants with postbaseline laboratory values will be included in these analyses. Physical examination, including vital signs (body temperature, respiratory rate, pulse rate, and blood pressure), and 12-lead ECG, recorded at baseline and after administration of study intervention. Analyses will be based on the Safety Analysis Set.

AE=adverse event, DLT=dose limiting toxicity, ECG=electrocardiogram, MedDRA=Medical Dictionary for Regulatory Activities, NCI-CTCAE=National Cancer Institute Common Terminology Criteria of Adverse Events, SAE=serious adverse event, SMC=Safety Monitoring Committee, TEAE=treatment-emergent adverse event.

Analyses for SMC Meetings:

During dose escalation the analysis will focus on safety and available PK data.

The Bayesian escalation approach will be applied to assist the SMC in the choice of the next dose level. The SMC will receive results of a Bayesian 2-parameter dose-toxicity model with overdose control, updated with the observed DLT data. The recommended next dose level will minimize the Bayesian Risk among all considered dose levels, while at the same time limiting the risk of overdose or excessive toxicity (Neuenschwander 2008). The target toxicity is 30%. Details of the model including the prior distribution and toxicity regions are described in [Appendix 10](#).

The following peposertib dose levels will be considered for escalation decisions: 30, 50, 100, 200, 400, 600, and 800 mg; 50 mg is the starting dose. Dose increases will not exceed 100% of the highest dose level considered safe at the time of escalation decision. The SMC may decide to deviate from the suggestion of the Bayesian escalation approach. Also, the SMC may decide to change the dosing regimen. In such a case the model will be extended, or a separate model will be set up.

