The purpose of this integrated analysis plan (IAP) is to document technical and detailed specifications for all analyses of data collected for the Phase Ib (dose escalation) protocol MS100036-0020. Results of the analyses described in this IAP will be included in the clinical study report (CSR). Additionally, the planned analyses identified in this IAP may be included in regulatory submissions or future manuscripts. Any post hoc, or unplanned analyses performed to

provide results for inclusion in the CSR but not identified in this prospective IAP will be clearly identified in the CSR.

The IAP is based on Section 9 (Statistical considerations) of the study protocol and protocol amendments and is prepared in compliance with International Conference on Harmonization (ICH) guideline E9.

Separate IAPs will document technical and detailed specifications for the analyses to be provided for safety monitoring committee (SMC) meetings.

Peposertib instead of peposertib (M3814) will be used in the current document.

5 Objectives and Endpoints

Objectives	Endpoints (Outcome Measures)	Endpoints (Outcome Measures) Timeframe	IAP section
Primary			
To define an MTD and RP2D of peposertib in combination with capecitabine and RT	Occurrence of dose limiting toxicities (DLT)	Time from first study intervention to end of chemoradiotherapy with a final assessment at 4 weeks after surgery	15. Safety Analyses
Secondary			
To evaluate safety and tolerability of peposertib in combination with capecitabine and RT	Occurrence of TEAEs and treatment-related adverse-events according to the NCI-CTCAE version 5.0 Occurrence of abnormalities (Grade ≥ 3) in laboratory test values, markedly abnormal vital sign measurements, and clinically significantly abnormal ECGs including clinically important increases in QT interval (QTcF)	Time from first study intervention to final assessment at 5 years	15. Safety Analyses
To explore antitumor activity of peposertib in combination with capecitabine and RT	Composite endpoint of pCR/cCR	Pathology evaluation of specimen after surgery (pCR) and clinical evaluation 1 to 2 weeks prior to surgery (cCR)	14. Efficacy Analyses

Objectives	Endpoints (Outcome Measures)	Endpoints (Outcome Measures) Timeframe	IAP section
	Disease-free Survival	Time from first study intervention to final assessment at 5 years	
	pCR	Pathology evaluation of specimen after surgery	
	cCR	Time from first study intervention until clinical evaluation 1 to 2 weeks prior to surgery	

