8.2 Definition of Analysis Populations and Subgroups

The analysis populations are specified below:

Table 1 Description of Analysis Sets

Population	Description
Enrolled	All participants who sign informed consent
Dose escalation (DE)	The DE Analysis Set will include all participants treated in dose escalation cohorts, who receive at least 80% of peposertib, 50% of capecitabine, and 80% of RT planned dose and complete the DLT period (5 or 5.5 weeks after start of treatment or for the entire duration of the treatment). The DE set will also include participants treated in dose escalation cohorts who experience a DLT during the DLT period regardless of the amount of each study intervention received/completion of the DLT period.
Full analysis set (FAS)	The FAS will include all participants who are enrolled in the study and received at least 1 dose of study intervention.
Safety (SAF)	The SAF analysis set will include all participants who receive at least 1 dose of study intervention. Participants will be analyzed according to the actual treatment they receive. In case of different doses received the dose with high number of administrations will be used as actual treatment.
Pharmacokinetics (PK)	The PK analysis set is defined as all participants who receive at least 1 dose of peposertib and have sufficient peposertib plasma concentration data to enable the calculation of at least 1 PK parameter. Sufficient concentration data is defined as at least 3 valid, post dose, concentration points in the PK profile to obtain any PK parameter.

DE=dose escalation, DLT=dose limiting toxicity, FAS=full analysis set, PK=pharmacokinetic, RT=radiotherapy, SAF=safety

Table 2 Summary of Analyses and associated Analysis Set

Analyses	ENR	SAF	FAS	DE	PK
Disposition	✓				
Baseline assessments		✓			
Past and concomitant therapies		✓			
Compliance and exposure		✓			
Primary endpoint: DLTs				✓	
Efficacy			✓		
Safety and tolerability		✓			
CCI					
Pharmacokinetics					✓
CCI					

DE=dose escalation, ENR=enrolled, FAS=full analysis set, PK=pharmacokinetic, SAF=safety

9 General Specifications for Data Analyses

Study intervention groups

Unless otherwise indicated all analyses will be presented separately for each dose level, and overall.

Data handling after cut-off date

Data after cut-off do not undergo the cleaning process, will not be included in SDTMs, and will not be displayed in any listings or used for statistical analyses or imputation.

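### For ECG interpretation, the SAP tabulates any abnormality visit by visit in participants with a normal baseline, which does not give the participant-level incidence of clinically significant abnormality that the secondary endpoint names

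*SAP*

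**What the plan says.** Protocol Table 6 and SAP 5 word the ECG part of the secondary safety endpoint identically, as the occurrence of "clinically significantly abnormal ECGs including clinically important increases in QT interval (QTcF").

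Protocol 8.2.3 has the Investigator interpret each ECG as normal or abnormal, and then adds: "If abnormal, it will be decided if the abnormality is clinically significant or not clinically significant".

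Protocol 9.4.2 (Table 13) names the endpoint but does not define the count. On ECGs it says only "12-lead ECG, recorded at baseline and after administration of study intervention".

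SAP 15.6.2 plans these ECG outputs:

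- descriptive statistics of the ECG parameters by dose level and visit;
- for interpretation, "The number of participants with normal ECGs at baseline and abnormal ECGs post baseline will be calculated by visit", shown by dose level and overall;
- frequency tables by dose level and overall, headed "Shift from normal baseline result to the worst on-treatment value" (bands up to above 500 ms) and "Worst on treatment mean QTcF increase from baseline" (bands up to above 60 ms);
- for replicate recordings, "For results interpretation, the worst Overall conclusion will be retained";
- one listing of all qualitative and one of all quantitative results.

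**The concern.** The endpoint is defined by a severity judgement (clinically significant) and by occurrence, which is a property of a participant over a period. The planned interpretation table has neither feature. A trivial abnormality and a significant one add the same amount to it, and a participant abnormal at three visits appears three times. A participant who starts with a minor abnormality and later has a significant one does not appear at all.

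The cohorts are small, so a single participant moves a dose level's percentage by a third. A reader of the study report who takes this table as the ECG safety result for a dose level could be misled in either direction. SAP 7, which lists departures from the protocol's planned analyses, does not mention this one.

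**Working it through.** The documents give no ECG frequency, so there is no figure to reproduce. The check compares the endpoint with the planned table and then illustrates the gap.

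**Endpoint against planned table**

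| Feature | Endpoint (protocol Table 6, SAP 5) | Interpretation table (SAP 15.6.2) |
|---|---|---|
| Event | Abnormal and clinically significant | Any abnormal |
| Unit | Participant, ever | Participant at each visit |
| Who can count | No baseline restriction stated | Normal baseline only |

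Two phrases might seem to close the gap, but do not.

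- *Overall.* SAP 9 says "all analyses will be presented separately for each dose level, and overall". Overall therefore means pooled over dose levels, not over visits.
- *Worst overall conclusion.* This rule sits under the instruction for duplicate or triplicate recordings at a time point. It selects within a time point, not across visits.

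The laboratory and vital-sign parts of the same endpoint do get participant-level summaries: shifts to worst on-treatment grade (SAP 15.4) and shifts by maximum on-treatment change (SAP 15.5).

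**Illustration in one cohort.** The planned cohort size is 3 (protocol 9.2).

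1. One participant has a normal baseline and one later non-significant abnormality. The table shows 1/3 = 33%; the endpoint count is 0/3.
2. Two participants with normal baselines each have one significant abnormality, at different visits. The table shows 1/3 and 1/3; the endpoint count is 2/3 = 67%.
3. One participant has a non-significant abnormality at baseline and a significant one later. The table shows 0; the endpoint count is 1/3 = 33%.

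**Illustration over the study.** Protocol Table 1 schedules ECGs at Screening, FD1 (before and 2 h after peposertib), FD11 and FD25/28. Taking the FD1 predose recording as baseline leaves three post-baseline time points. With counts a, b, c at those points among N participants, the number with at least one event satisfies

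max(a, b, c) ≤ participants ≤ min(N, a + b + c).

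The synopsis gives 19 participants treated as of 06 May 2021. Assume that all 19 had a normal baseline and that there are 2 abnormal ECGs at each time point:

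- lower bound: max(2, 2, 2) = 2, so 2/19 = 10.5%;
- upper bound: min(19, 2 + 2 + 2) = 6, so 6/19 = 31.6%.

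The by-visit table shows 2/19 three times in either case. It cannot tell these situations apart, and it cannot say how many of the findings were significant.

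**QTcF part.** The two frequency tables use the worst on-treatment value, so each participant is classified once. The increase table is explicitly for QTcF. The absolute-value bands are in milliseconds and start from a normal baseline result. Neither document says which band is a clinically important increase.

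**The case against.** A reader might infer that the ECG endpoint is never summarised and that everything is counted visit by visit. The documents do not support that. The endpoint expressly includes QTcF increases, and the sentence after the quoted one in SAP 15.6.2 plans participant-level QTcF tables by dose level and overall. The gap is confined to ECG interpretation.

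Four further arguments carry some weight.

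- *Adverse event route.* Protocol Appendix 7 makes an abnormal ECG an adverse event if it comes with signs or symptoms, leads to discontinuation, or is otherwise medically important in the Investigator's view. Such events reach the participant-level TEAE tables. This overlaps with clinical significance but is a different criterion, so it is a partial substitute.
- *Listing.* Every qualitative result is listed. With 19 participants and three time points there would be about 19 × 3 = 57 scheduled conclusions, so a hand count is feasible. A listing is still not a planned summary of a named endpoint.
- *Data.* Protocol 8.2.3 says that significance will be decided and that the reason for the abnormality goes on the eCRF. It implies, but does not plainly state, that the significance judgement itself is an eCRF item. This stands as a condition on the fix.
- *Consequence.* The study is exploratory with no formal tests (protocol 9.1), Phase II will not be performed, and dose escalation rests on DLT data and separate analyses for the SMC. No decision described in the documents turns on this table. Protocol Table 13 prescribes no ECG count, so the SAP contradicts no stated method. This limits the severity but does not supply the missing summary.

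**Conclusion.** The point holds for the interpretation component only. Followed as written, the SAP tabulates a different event from the endpoint, gives no on-treatment incidence per participant, and excludes participants with a non-significant baseline abnormality. The error can run either way: in a cohort of 3, one participant affected by the severity or baseline issue shifts the result by 33 percentage points.

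The size in the actual data is unknown. The 10.5% to 31.6% range rests on assumed counts and on all 19 participants having a normal baseline. Nothing shows that any result has been misreported, and the planned table does not claim to be the endpoint's incidence.

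The QTcF component is covered per participant, with one open item: which categories are clinically important. This is worth correcting because a named secondary endpoint should have a planned summary, but it does not threaten the study's primary conclusions.

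**What to change.** In SAP 15.6.2:

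1. Add the number and percentage of SAF participants with at least one on-treatment ECG whose worst overall conclusion is abnormal and clinically significant, by dose level and overall. Show separately any participant already in that state at baseline.
2. Add a shift table from baseline to worst on-treatment conclusion, with the categories normal, abnormal not clinically significant, and abnormal clinically significant.
3. State which of the existing QTcF categories count toward the endpoint.
4. Keep the by-visit table as supportive.

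Use the on-treatment period as defined in SAP 9 for both new outputs, so that they cover the same recordings. First confirm that the ECG eCRF page holds the significance judgement, as protocol 8.2.3 implies. If it does, the cost is one or two extra tables and no new data collection.

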In conclusion, emerging clinical safety data from studies EMR100036-001 and EMR100036-002, and supportive results of a comprehensive series of nonclinical safety pharmacology, PK, and toxicology studies, as well as primary and secondary PD findings support continued clinical development of peposertib in combination with RT, and/or chemotherapy.

3 Objectives and Endpoints

Study objectives and endpoints are provided in [Table 6](#). Statistical analysis of the endpoints is described in [Section 9.4](#).

Table 6 Study Objectives and Endpoints

Objectives	Endpoints (Outcome Measures)	Endpoints (Outcome Measures) Timeframe
Primary		
To define an MTD and RP2D of peposertib in combination with capecitabine and RT	Occurrence of dose limiting toxicities	Time from first study intervention to the end of CRT with a final assessment at 4 weeks after surgery
Secondary		
To evaluate safety and tolerability of peposertib in combination with capecitabine and RT	
 • Occurrence of TEAEs and treatment-related adverse events according to the NCI-CTCAE version 5.0 • Occurrence of abnormalities (Grade ≥ 3) in laboratory test values, markedly abnormal vital sign measurements, and clinically significantly abnormal ECGs including clinically important increases in QT interval (QTcF) 	Time from first study intervention to final assessment at 1 year
To explore antitumor activity of peposertib in combination with capecitabine and RT	
 • Composite endpoint of pCR/cCR • Disease-free Survival • pCR • cCR • Local recurrence and/or distant metastasis • Neoadjuvant rectal score 	
 • Pathology evaluation of specimen after surgery (pCR) and clinical evaluation 1 to 2 weeks prior to surgery (cCR) • Time from first study intervention to final assessment at 1 year • Pathology evaluation of specimen after surgery • Time from first study Intervention until clinical evaluation 1 to 2 weeks prior to surgery • Time from surgery to final assessment at 1 year • Pathology evaluation of specimen after surgery
To assess the PK of peposertib	PK profile of peposertib in terms of PK parameter estimates (e.g. C _{max} , AUC _{0-t} , t _{max} , CL/f, Vz/f, t _{1/2})	FD1 and FD9

CCI

cCR=Clinical Complete Response, CRT=chemoradiotherapy, CCI [REDACTED]
[REDACTED] ECG=electrocardiogram, FD=fraction day, MTD=maximum tolerated dose, NCI-CTCAE=National Cancer

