5.2 Exclusion Criteria

Participants are excluded from the study if any of the following criteria apply:

Medical Conditions

1. History of any other significant medical disease or psychiatric conditions that might in the assessment of the Investigator preclude safe participation in the study
2. History of difficulty swallowing, malabsorption, or other chronic gastrointestinal disease or conditions that may hamper compliance and/or absorption of the study intervention
3. Unstable cardiovascular function within 6 months prior to enrollment (i.e. ischemia, symptomatic angina, congestive heart failure, Class III to IV New York Heart Association uncontrolled conduction abnormalities including a history of long QTc syndrome [QTcF > 480 ms] and/or pacemaker, or myocardial infarction)
4. Hypertension uncontrolled by medication (i.e. systolic blood pressure \geq 150 mmHg and diastolic blood pressure \geq 90 mmHg)
5. History of other malignant disease within the past 5 years, other than successfully treated basal carcinoma of the skin or carcinoma in situ of the cervix
6. Known human immunodeficiency virus positivity, known active viral hepatitis, current alcohol abuse, or cirrhosis
7. Ongoing active infection or treatment with a live attenuated vaccine within 4 weeks of dosing.

Prior/Concomitant Therapy

8. Previous radiation therapy to the pelvis
9. Concurrent use of other anticancer therapy
10. Major surgical intervention within 4 weeks prior to the first dose of study intervention. Biopsy(s) to establish the diagnosis for rectal cancer is permitted. Diverting ostomy is permitted

11. Concomitant or prior use of medications or herbal supplements, known to be strong inhibitors of cytochrome P450 (CYP) 3A and/or CYP2C19, unless use can be discontinued 1 week prior to receiving the first dose of study intervention. Concomitant or prior use of medications or herbal supplements, known to be strong inducers of CYP3A and/or CYP2C19, unless use can be discontinued at least 3 weeks prior to receiving study intervention. Concomitant or prior therapy use of medications or herbal supplements mainly metabolized by CYP3A with a narrow therapeutic index must be stopped at least 1 day prior to receiving study intervention
12. Concomitant use of H₂-blocker or proton pump inhibitors (PPIs) (or unable to stop at least 5 days prior to the first treatment). Note that calcium carbonate is acceptable

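### SAP 15.6.2 limits the abnormal-ECG count and the only table with a QTcF >500 ms row to participants with an undefined normal baseline, although the ECG endpoint covers the whole safety set

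*SAP*

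**What the plan says.** The secondary safety endpoint (Protocol Synopsis and Section 3, Table 6) is the occurrence of, among other things, "clinically significantly abnormal ECGs including clinically important increases in QT interval (QTcF"). It carries no condition on the baseline ECG. Protocol Table 13 assigns the analysis to the Safety Analysis Set and gives no ECG categories of its own.

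SAP 15.6.2 names the SAF set as its population and plans three categorical outputs:

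- An abnormal-ECG count: "The number of participants with normal ECGs at baseline and abnormal ECGs post baseline will be calculated by visit".
- An absolute-value table: "Shift from normal baseline result to the worst on-treatment value", with rows ≤450, >450–480, >480–500 and >500 ms. The parameter is not named; the cut-offs imply QTcF.
- An increase table: "Worst on treatment mean QTcF increase from baseline", with rows ≤30, >30–60 and >60 ms and no baseline restriction.

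It also plans visit summaries by dose level, "using descriptive statistics (see [Section 9](#)) for absolute values and absolute change from baseline", and listings of all qualitative and quantitative ECG results. With triplicates, the mean is used for quantitative parameters and the worst overall conclusion for interpretation.

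The only QTcF figure in eligibility is in Protocol 5.2, criterion 3, on unstable cardiovascular function: "uncontrolled conduction abnormalities including a history of long QTc syndrome [QTcF > 480 ms"]. On reading the trace, Protocol 8.2.3 says: "The Investigator will judge the overall interpretation as normal or abnormal". For an abnormal trace, "it will be decided if the abnormality is clinically significant or not clinically significant".

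**The concern.** A participant whose baseline QTcF is already raised needs the smallest rise to pass 500 ms. Under at least two natural readings of the SAP, that participant is left out of the only table that counts values above 500 ms. Someone reading that table in a section headed with the safety set would take a zero in the >500 ms row to mean zero among all treated participants, and it might not be.

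The qualitative count has a related weakness. It records any abnormal trace after a normal baseline, whereas the endpoint concerns clinically significant abnormality, a judgement the sites already have to make. A participant whose baseline was abnormal but not clinically significant, and who becomes clinically significantly abnormal on treatment, is in no count.

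The SAP does not treat its other safety data this way. The laboratory shift tables (15.4) keep Low or High baselines with Missing and Overall categories. The vital-sign tables (15.5) keep raised baselines, for example systolic pressure <140 and ≥140 mmHg. No reason is given for handling ECGs differently.

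**Working it through.** The plan states no figure to reproduce, so the check is to place example participants in the planned tables.

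**Inputs.** Absolute and increase rows from SAP 15.6.2; the 480 ms figure from Protocol 5.2; planned cohort size 3 and 19 treated participants as of 06 May 2021 from the Protocol Synopsis.

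**Step 1: place pairs of baseline and worst on-treatment QTcF (ms).** Rise = worst − baseline.

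| Baseline → worst | Rise | Increase row | Absolute row if normal is ≤450 | Absolute row if normal is ≤480 |
|---|---|---|---|---|
| 440 → 505 | 65 | >60 | >500 | >500 |
| 451 → 505 | 54 | >30–60 | not in table | >500 |
| 475 → 504 | 29 | ≤30 | not in table | >500 |
| 480 → 501 | 21 | ≤30 | not in table | >500 |

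Under a third reading, where normal is the investigator's overall interpretation, the last three pairs are counted only if the baseline trace was read as normal.

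**Step 2: does the increase table fill the gap?** In whole milliseconds, the smallest rise that passes 500 ms is 501 − baseline.

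- Baseline 451: 501 − 451 = 50. Baseline 470: 501 − 470 = 31. Both fall in >30–60 ms, which does not show that 500 ms was passed.
- Baseline 471: 501 − 471 = 30. Baseline 480: 501 − 480 = 21. Both fall in the lowest row, ≤30 ms.

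The closer the baseline is to 480 ms, the less the increase table shows.

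**Step 3: do the adverse event tables fill it?** Not reliably. Under Protocol Appendix 7, an abnormal ECG finding is not reported as an AE unless it comes with signs or symptoms, leads to discontinuation of study intervention, or is otherwise judged medically important by the investigator.

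**Step 4: size of one case.** 1/3 = 33% of a planned cohort; 1/19 = 5.3% of those treated by 06 May 2021.

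**Step 5: after the fix.** With all participants tabulated by baseline category, all four pairs fall in the >500 ms row.

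**The case against.** The strongest reply is that nothing is hidden. Every ECG value is listed, with triplicate means and a pre/on/post flag. The visit summaries cover all participants and include the minimum, median and maximum; with three participants at a visit, those show every value. The increase table is unrestricted. The gap also depends on an undefined word: if normal means ≤480 ms, baselines of 451–480 ms are all counted. The study is exploratory, treatment is complete, and no decision rule in the two documents uses this table.

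All of this is right, and it limits the point to counting. It does not answer it. A visit maximum is not a number of participants. It covers scheduled visits only, and SAP Section 9 shows a visit only where all later visits have at least 3 participants. A listing gives no incidence by dose level. Where a table turns on a word, the SAP should define it, and its own first boundary is 450 ms.

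Some stronger inferences are tempting and should not be drawn:

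- That a value above 500 ms would go unreported. It would be in the listings.
- That 480 ms is an entry ceiling on the screening ECG. Criterion 3 concerns a history of long QTc syndrome. What can be said is that eligibility states no lower QTcF limit.
- That one abnormal trace of three removes a participant from both tables. The worst-of-triplicate rule applies to interpretation; quantitative values use the mean. The millisecond table is affected only if normal means the overall reading.
- That the normal-to-abnormal count is the endpoint, so that trivial findings become endpoint events. The SAP does not label it so.

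**Conclusion.** The point holds as a gap in the tables. SAP 15.6.2 restricts two of its three categorical ECG outputs to a normal baseline that it does not define, while the endpoint and the section's own population carry no such limit. If normal means ≤450 ms or the investigator's reading, a participant with a non-normal baseline who passes 500 ms is in no absolute-category count, and may sit in the lowest increase row (475 to 504 ms, +29 ms).

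The documents report no baseline ECG or QTcF results, so the number affected is unknown and could be zero; any estimate of it would be unsupported. A single case would matter mainly in the display by dose level, where cohorts are planned at 3. Under the ≤480 ms reading, the gap for baselines of 451–480 ms closes, and what remains is the missing definition and the absence of a count of clinically significant abnormalities across all baseline groups.

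**What to change.** In SAP 15.6.2:

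1. Delete the word normal from the absolute-value table and name QTcF as its parameter. Tabulate worst on-treatment QTcF category for all SAF participants by dose level and overall, cross-classified by baseline QTcF: ≤450, >450–480, >480 ms and missing.
2. Keep the normal-to-abnormal count if wanted. In addition, tabulate all participants with a clinically significant abnormal post-baseline ECG by baseline interpretation: normal, abnormal not clinically significant, abnormal clinically significant, missing. No baseline subgroup is then dropped.

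The cost is SAP and table-shell wording. The QTcF values and the investigator's judgement of significance are already collected under the protocol.
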